We do not anticipate large amounts of missing data. If the missing data exceeds 5%, sensitivity analyses will be performed using a pattern mixture approach and multiple imputations will be conducted to compare the sensitivity of conclusions to varying assumptions about the missing data, notably whether data are missing at random (MAR) or missing not at random (MNAR) to allow for an assessment of both random and systemic bias. The variation of the primary outcome by different assumptions of missing data will be presented.

Compliance

We will conduct a Complier Average Causal Effects (CACE) analysis using an instrumental variable framework to explore the impact of compliance on the primary outcomes at different levels of compliance. CACE weighs the intention-to-treat (ITT) treatment effect by the proportion of compliance, this allows the estimation of unbiased treatment effects and maintains the allocation in the analysis. The CACE analysis will be implemented using a two-stage least squares (2SLS) approach clustering the standard errors, where the first stage models compliance as a function of the randomised treatment assignment, and the second stage models the outcome as a function of the predicted compliance from the first stage and other covariates.

Compliance will be measured at the school level through a binary variable, compliance (Yes/No). Compliance for those schools in the intervention arm will be assessed based on the level of engagement. Section 5 discusses an engagement tool in more detail. The engagement tool assesses level of schools engagement with the delivery of TISUK intervention across five key dimensions:

- Individual Training,
- Whole Staff Training,
- Consultancy,
- Reflective Supervision,
- Webinars.

Each dimension is scored based on specific criteria, such as the number of staff trained, attendance at meetings, and utilisation of resources. The tool uses a point-based system, with 100 points possible across all dimensions. The final score is calculated as a percentage, with clear thresholds for interpretation:

- up to 50% indicates poor engagement,
- 51-75% moderate engagement,
- 76-90% good engagement, and
- 90-100% excellent engagement.

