2.3 Analysis

The analysis was chosen before collecting baseline survey data. The syntax in Stata© is included at the end of this section. The analysis will be conducted using an analysis by intention to treat (ITT) and will include all available data, maintaining participants as members of their allocated group. The following research questions will be addressed:

Pupil level

and baseline testing process. As a result, there is a difference of 2 schools between the intervention and control groups, partly because randomisation occurred over two waves of recruitment.

⁹ This is the achieved sample size for the primary outcome (Externalising behaviours-SDQ)

- ERQ1: What is the mean difference in externalising behaviour, measured by the Strengths and Difficulties Questionnaire (SDQ) subdomains of Conduct Problems and Hyperactivity, between CYP in intervention settings receiving TISUK training and CYP in control settings receiving business as usual at follow-up?
- ERQ2: What is the mean difference in internalising behaviour, measured by the Strengths and Difficulties Questionnaire (SDQ) subdomains of Emotional Problems and Peer Problems, between CYP in intervention settings receiving TISUK training and CYP in control settings receiving business as usual at follow-up?
- ERQ3: What is the mean difference in prosocial behaviour, measured by the SDQ subdomain of Prosocial behaviour, between CYP in intervention settings receiving TISUK training and CYP in control settings receiving business-as-usual at follow-up?
- ERQ4: What is the mean difference in Total Difficulties, measured by the SDQ subdomain of Conduct Problems, Hyperactivity, Emotional Problems and Peer Problems, between CYP in intervention settings receiving TISUK training and CYP in control settings receiving business-as-usual at follow-up?
- ERQ5: What is the mean difference in non-psychotic psychological distress, measured by the General Health Questionnaire (GHQ), between CYP in intervention settings receiving TISUK training and CYP in control settings receiving business as usual at follow-up?
- ERQ6: What is the mean difference in well-being, measured by the Short Warwick Edinburgh Well-being Scale (SWEMWBS), between CYP in intervention settings receiving TISUK training and CYP in control settings receiving business as usual at follow-up?

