- ERQ17: What is the difference in the percentage of CYP exclusions at the school level between schools in the intervention setting receiving TISUK training and schools in control settings receiving business as usual at follow-up?
- ERQ18: What is the difference in the percentage of CYP school attendance in the targeted years at the school level between schools in the intervention setting receiving TISUK training and schools in control settings receiving business as usual at follow-up?
- ERQ19: What is the difference in the percentage of CYP school suspensions/exclusions/attendance in the targeted years at the school level between schools in the intervention setting receiving TISUK training and schools in control settings

receiving business as usual at follow-up, considering sub-group analysis by sex, ethnicity, and free school meal (FSM) eligibility?

As evidence suggests, the distribution of the externalising behaviour subscale of the SDQ is normally distributed (Caldwell et al., 2021); thus, the primary analysis will take the form of a multilevel model with random effects at school considering pupils are nested within schools and this may introduce variation. The model will include the binary treatment variable and be adjusted for baseline stratification covariates¹⁰ and the baseline value of the outcome.

We are employing a random-effects approach to model the cluster-level effects at the school level in our trial. This approach allows us to treat schools as random samples from a broader population, enabling the generalizability of our findings beyond just the sampled schools. Moreover, the random-effects model incorporates partial pooling or shrinkage, which can lead to better predictions of school-level effects compared to a fixed-effects approach. Crucially, with a sufficient number of school clusters (more than 10 or 20) in our sample, we can reliably estimate the between-cluster variance and make valid inferences about the variability of school-level effects, providing insights into the impact of school-level factors on the outcome of interest (Rabe-Hesketh & Skrondal, 2008).

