Secondary outcomes will be assessed similarly by establishing diagnostic plots to explore the distribution and identify the most appropriate regression approach, including stratification factors and baseline covariates within a multilevel model. These plots include residual plots to check for violations like non-linearity and heteroscedasticity, normal probability plots to assess the normality of residuals, and histograms of residuals to identify potential outliers.

Outcomes at the individual level (CYP and school staff) will be analysed using multilevel modelling, while outcomes at the school level will be done through linear regression. Table 5 sets out the statistical analysis for each outcome by level.

Table 5 Statistical analysis by outcome and level

Outcome	Level	Model	Covariates
Primary outcome Externalising behaviour	CYP	Multilevel model	Pre-treatment scores of outcomes at CYP level

¹⁰ This refers to the binary variable indicating whether the school is above or below the median proportion of FSM6 students

Secondary outcomes Internalising behaviour Non-psychotic psychological distress Well-being Sense of connectedness Exclusions, suspensions and attendance at individual (CYP) level			Demographic factors (sex, FSM status) at CYP level
Secondary outcomes Attitudes related to TIC Well-being	School Staff	Multilevel model	Pre-treatment scores of outcomes at staff level
Secondary outcomes Staff retention Staff sickness Exclusions & suspensions of CYP School attendance of CYP	School	Linear regression (OLS)	Pre-treatment scores of outcomes at the school level

The syntax in Stata© would be as below, using the ‘mixed’ command:

```
Full adjusted model: mixed post-treatment_outcome TISUK baseline_outcome fsm || school_id
```

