2.3.8 Missing data

The proportion of missing data and patterns of missingness will be examined for the primary outcome only, externalising behaviour at six months post-randomisation. Levels of missing data will be reported along with any systematic occurrences of missing data observed in the dataset.

In trials, some participants are inevitably lost to follow-up. The sample size estimation assumed that 20%¹² of participants would not provide an evaluable 6-month follow-up assessment. We will explore the mechanism of missing data to establish whether the data can be considered missing completely at random or missing at random. For each arm, we will present baseline data for those who were followed up at 6 months and those who were lost to follow-up. A logistic regression analysis will be conducted to explore any systematic differences between the allocated groups. If the regression model does not identify any predictor variables, it suggests that the missing data can be considered missing at random.

To avoid loss of efficiency, missing outcome values will be imputed using multiple imputation if the proportion of missing data is greater than 5% and less than 40%. When less than 5% of data is missing, the proportion is considered negligible, and missing observations will be excluded. Multiple imputation methods may perform less well when a substantial amount of data is missing (e.g., more than 40% for the primary analysis). In such cases, the assumptions underlying the imputation become less plausible, and the interpretative limitations of the trial data will be discussed in the results section.

An initial variable reduction analysis will explore the relationship between all potentially prognostic baseline variables and whether a follow-up data point is missing. Only variables where there is an association (p-value > 0.10) will be included in the imputation model.

The number of imputations will be determined to ensure at least 96% statistical efficiency (RE), according to the formula below, where l is the fraction of missing values and M is the number of repetitions:

$$RE = \left(1 + \frac{\lambda}{M}\right)^{-1}$$

¹² This accounts for 10% attrition and 10% non-consent rate

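### The primary model needs a baseline score that 23.9% of pupils lack, and the SAP imputes only outcomes, so pupils with a follow-up score but no baseline score drop out of the analysis

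*SAP*

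**What the plan says.** **Analysis set.** SAP 2.3 adopts intention to treat and says that the analysis "will include all available data, maintaining participants as members of their allocated group". Protocol 4.1 says the same in substance.

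**Model.** SAP 2.3 adjusts the primary multilevel model for the FSM6 stratum "and the baseline value of the outcome". The equation in SAP 2.3.1 includes the pupil's baseline value, and the Stata line is "mixed post-treatment_outcome TISUK baseline_outcome fsm || school_id". It has no missing-data indicator and no imputation prefix.

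**Missing data.** SAP 2.3.8 is written around loss to follow-up. It says that "patterns of missingness will be examined for the primary outcome only", and that "missing outcome values will be imputed using multiple imputation" when more than 5% and less than 40% are missing. Below 5%, missing observations are excluded. Baseline variables appear only as predictors of missing follow-up and as candidates for the imputation model. The section ends by carrying the primary model into the imputation, without saying that baseline values are imputed.

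**Protocol.** Protocol 4.1 is more general: "If the missing data exceeds 5%, sensitivity analyses will be performed using a pattern mixture approach and multiple imputations will be conducted". It names no covariates.

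**Baseline data in hand.** SAP Table 6 reports the baseline externalising score for 6,179 control pupils (2,232 missing) and 7,214 intervention pupils (1,983 missing).

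**The concern.** A regression fitted with `mixed` uses only rows in which every covariate is present. A pupil who answers at follow-up but has no baseline score is therefore excluded, although the outcome was observed. Imputing outcomes does not bring that pupil back, because the baseline term is still missing when the model is fitted to each imputed data set.

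The gap already exists in the data, at nearly five times the 5% that SAP 2.3.8 treats as negligible. The diagnostics planned there would not show it: they compare baseline data for pupils followed up with those lost, and pupils without a baseline SDQ score are absent from any step that uses it.

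At stake are some precision and a clear statement of whom the estimate describes. The analysis population would be pupils who answered twice, which the SAP does not declare.

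**Working it through.** **1. Are the bracketed counts in Table 6 additional to n?** 6,179 + 7,214 = 13,393. This is exactly the total in Table 4, whose footnote says "This is the achieved sample size for the primary outcome". So n counts pupils with a score, and the missing counts come on top.

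**2. Share without a baseline score.**

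| | Observed | Missing | Total | Missing share |
|---|---|---|---|---|
| Control (as labelled in Table 6) | 6,179 | 2,232 | 8,411 | 26.5% |
| Intervention (as labelled in Table 6) | 7,214 | 1,983 | 9,197 | 21.6% |
| Both | 13,393 | 4,215 | 17,608 | 23.9% |

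**3. Are the arm labels secure?** No. Table 4 gives 6,391 for intervention and 7,214 for control, so 7,214 sits in the opposite arm from Table 6. The Table 4 arms sum to 6,391 + 7,214 = 13,605, which is 212 more than its own total of 13,393. The overall 23.9% uses only Table 6 and does not depend on which label is right. The arm-specific rates do.

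**4. Reproducing the plan's MDES.** Using the SAP 2.2 formula with 78 schools, 166 pupils per school, ICC 0.015, no covariate gain, P = 0.5, two-sided alpha 0.05, power 0.8 and a t multiplier on 76 degrees of freedom, the MDES is 0.0930. Table 4 states 0.094, about 1% away. The SAP's figure thus already rests on pupils with a baseline score.

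**5. Precision cost.** The variance of the contrast is proportional to ICC + (1 − ICC)/m. Pupils per school are 13,393/78 = 171.7 with a baseline score and 17,608/78 = 225.7 in all. Assume that both groups respond at follow-up at the same rate.

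- Full follow-up: √[(0.015 + 0.985/171.7)/(0.015 + 0.985/225.7)] = √(0.02074/0.01936) = 1.035.
- 20% follow-up loss (m = 137.4 against 180.6): √(0.02217/0.02045) = 1.041.

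MDES by assumed follow-up loss (P = 40/78, t multiplier):

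| Follow-up loss | Pupils without baseline kept | Dropped | Ratio |
|---|---|---|---|
| 0% | 0.0895 | 0.0926 | 1.035 |
| 10% | 0.0906 | 0.0940 | 1.038 |
| 20% | 0.0919 | 0.0957 | 1.041 |
| 30% | 0.0937 | 0.0979 | 1.045 |

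**6. Allowing for baseline adjustment.** Suppose a pupil-level pre-post correlation of 0.6 (assumption; the documents give none) and full follow-up. Residual variance is 0.985 × 0.64 = 0.630 for pupils with a baseline score and 0.985 for the 4,215/78 = 54.0 per school without. Information per school is 171.7/0.630 = 272.4 without the latter, and 272.4 + 54.0/0.985 = 327.2 with them. The ratio becomes √[(0.015 + 1/272.4)/(0.015 + 1/327.2)] = √(0.01867/0.01806) = 1.017. If baseline also explained 60% of the between-school variance (0.015 × 0.4 = 0.006), it would be √(0.00967/0.00906) = 1.033. The reduction thus depends on adjustment working mainly at pupil level.

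**7. The 40% limit.** If baseline and follow-up loss were independent (assumption), 20% follow-up loss would leave 1 − 0.761 × 0.8 = 39% of pupils incomplete, and 30% loss would leave 1 − 0.761 × 0.7 = 47%. SAP 2.3.8 does not say whether its limit counts missing outcomes or incomplete pupils, so the choice of denominator could decide whether imputation is done.

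**The case against.** The strongest reply is that 23.9% is not the share dropped. Only pupils with a follow-up score and no baseline score are lost for this reason, and the documents do not count them. Table 6 does not define N. The implied 226 pupils per school exceeds the average year group of 197 to 200 used in the sample-size section, so N may be the full Year 8 roll. Parents could opt pupils out before baseline and pupils had to assent (Protocol 4 and 9), and the sample size assumed that 20% would not consent. Opted-out pupils would have no follow-up and are not available data. This stands: 4,215 is an upper bound.

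A reader might infer three stronger points that the documents do not support:

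- **Bias between arms from 26.5% against 21.6%.** Protocol 3.2 places baseline before allocation, so allocation cannot have caused the gap, and its direction is insecure while Tables 4 and 6 disagree. Multiplying the 5-point gap by an assumed 0.3 SD difference gives 0.015 SD. That also assumes balanced full rolls, follow-up from every such pupil and no help from adjustment.
- **Loss of higher-need pupils.** This is plausible, but neither document says who lacks a baseline score or why.
- **A breach of intention to treat.** Conditioning on a pre-allocation measurement keeps pupils in their allocated arm. What fails is the promise to use all available data.

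It can also be said that the Stata line is indicative, that Protocol 4.1 does not limit imputation to outcomes, and that the primary model carried into the imputation contains baseline. None of these gives a rule for a pupil with follow-up but no baseline score.

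**Conclusion.** The point holds as a cheap improvement. Following the SAP as written excludes every pupil with a follow-up score but no baseline score, and neither document brings them back.

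The number lost lies between 0 and 4,215. With equal follow-up response in both groups, the cost is about 3.5% to 4% in standard error for follow-up loss between 0% and 20%, before baseline adjustment. It falls to about 1.7% under the assumed pupil-level correlation of 0.6 with no school-level gain. If these pupils respond less often than the rest, the cost is smaller still. This does not threaten the trial's power.

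The conclusion that the harm is precision and population, not arm bias, rests on baseline preceding allocation in every school. Protocol 3.2 says so. Protocol 3.3 dates the second allocation to early January 2024 but describes testing in those schools as running through December and January, so the team should confirm the order school by school. The arm-specific rates should not be relied on until Tables 4 and 6 are reconciled.

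**What to change.** Amend SAP 2.3 and 2.3.8 before follow-up data are examined:

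1. Define N in Table 6, separating opt-outs from eligible pupils who did not respond, and reconcile the arm counts in Tables 4 and 6.
2. Define the primary analysis set as eligible Year 8 pupils in randomised schools with a follow-up score, with a stated rule for pupils who joined after allocation.
3. Pre-specify one method for a missing baseline score in the primary model: either the overall mean plus a missing indicator, or baseline SDQ imputed jointly with the outcome in the multilevel imputation. The first is acceptable here because the covariate is measured before allocation. The second can draw on the administrative records also collected at baseline.
4. State the denominator for the 5% and 40% limits.
5. Report baseline missingness by arm, and the complete-pair analysis as a sensitivity analysis.

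The cost is SAP wording and a few lines of code, with slightly less covariate adjustment for pupils who have no baseline score. No new data collection is needed.

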	70	0.1272	0.1284	0.1298	0.1317	0.1341
	60	0.1374	0.1385	0.1402	0.1422	0.1449

Rationale for Targeting 100 Schools

Targeting 100 schools and 16,000 students is justified by several considerations. First, a larger pool of schools increases the likelihood of recruiting a diverse population of school types (e.g., school-level of deprivation, FSM, different socioeconomic backgrounds) and student demographics, enabling robust subgroup analyses and generalizability of findings across various contexts. Second, a large overall sample size enhances statistical power to detect smaller but potentially meaningful intervention effects, minimising the risk of false negatives and providing reliable findings to inform future interventions. Third, the target sample size was selected to ensure sufficient power for the quasi-experimental design (QED) analysis focused on a targeted subgroup of students. Lastly, a larger sample size accommodates the cluster randomised trial design, accounting for potential clustering effects and maintaining adequate power for the primary analysis.

Table 4 displays the minimum detectable effect in the protocol according to the assumed parameters, target sample size, and the respective effect size after randomisation driven by the achieved number of responses on the primary outcome. Thus, while the MDES in the protocol is an estimation from the assumptions, the MDES estimated in the column 'Randomisation' corresponds to the actual achieved sample size at baseline in the primary outcome from the schools that were randomised. As we are adopting an intention-to-treat approach, the estimation includes responses from 4 schools that dropped out after randomisation.⁵ Those four schools that dropped out belong to the intervention group.

⁵ This means that now the number of schools in the trial are 74 with 4 dropping out from the intervention group after randomisation

Table 4 Sample size calculations and effects size

		Protocol	Randomisation
Minimum Detectable Effect Size (MDES)		0.1064	0.094
Pre-test/ post-test correlations	level 1 (participant)	n/a	n/a
	level 2 (cluster)	n/a	n/a
Intracluster correlations (ICCs)	level 1 (participant)	n/a	n/a
	level 2 (cluster)	0.03	0.015
Alpha		0.05	0.05
Power		0.8	0.8
One-sided or two-sided?		Two-sided	Two-sided
Average cluster size		160⁶	166⁷
Number of clusters	intervention	50	40
	control	50	38
	Total	100	78 ⁸

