2.3.6 Longitudinal follow-up analyses

There is one follow-up analysis at the end of the intervention for all outcomes, 15 months after randomisation, which follows the outcome analysis described above in sections 2.3.1 and 2.3.2.

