The statistical model and assumptions made in the analysis of the primary outcome will also be implemented in the multiple imputation procedures. If it is suspected that data is missing not at random or if the pattern of missing data is associated with trial allocation, sensitivity analysis will be performed using a pattern mixture approach with mixed modelling and multiple imputation to compare the sensitivity of conclusions to varying assumptions about the missing value mechanism.

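### SAP 2.3.8 prints the imputation screening threshold the wrong way round, so auxiliary predictors of missing follow-up are left out of the imputation model

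*SAP*

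**What the plan says.** SAP 2.3.8 imputes the primary outcome when between 5% and 40% is missing. To choose the imputation variables, a preliminary analysis "will explore the relationship between all potentially prognostic baseline variables and whether a follow-up data point is missing". The selection rule follows: "Only variables where there is an association (p-value > 0.10) will be included in the imputation model". The end of the section adds that the model and assumptions of the primary analysis also apply in the imputation. SAP 2.3 and 2.3.1 define that model as arm, baseline score, the FSM6 stratum and a school random intercept.

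Four other statements in 2.3.8 bear on the point:

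- The outcome is dated as "externalising behaviour at six months post-randomisation", and six months appears twice more. SAP 2.3.6 says: "There is one follow-up analysis at the end of the intervention for all outcomes, 15 months after randomisation". SAP 2.1 and Protocol section 4 also give 15 months.
- On the mechanism: "If the regression model does not identify any predictor variables, it suggests that the missing data can be considered missing at random".
- The section says the sample size allowed for 20% loss, which a footnote splits into 10% attrition and 10% non-consent. SAP 2.2 used 10% attrition and 20% non-consent.
- The pattern-mixture analysis is run "If it is suspected that data is missing not at random", or if the pattern of missingness is associated with allocation. Protocol 4.1 has a simpler trigger: "If the missing data exceeds 5%, sensitivity analyses will be performed using a pattern mixture approach".

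**The concern.** An imputation model should contain the variables that predict missingness and, above all, those that also predict the outcome. The printed inequality selects the opposite set and contradicts the sentence it sits in. A SAP is the pre-specified instruction, and reversing the sign once follow-up data have been seen would be a post-hoc change to how the primary outcome is imputed.

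Missingness related to arm is plausible here. SAP 2.2 reports that four schools withdrew after randomisation and adds: "Those four schools that dropped out belong to the intervention group". That is 4 of 40 against 0 of 38. The pupil survey is completed in school (Protocol section 4), so attendance and exclusion could affect who responds, and the programme aims to change both. Attendance, suspension and exclusion records are already collected, and SAP 3.3 uses them as matching covariates in the embedded study. They are natural auxiliary variables, yet any of them that strongly predicts missing follow-up would be screened out.

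**Working it through.** **1. What the printed rule selects.** For a variable whose test statistic has expected value z, the probability of being kept is P(p > 0.10) = Φ(1.645 − z) − Φ(−1.645 − z).

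| Expected z | Kept under p > 0.10 |
|---|---|
| 0 (unrelated to missingness) | 90% |
| 1 | 74% |
| 2 | 36% |
| 2.8 | 12% |
| 4 | 1% |

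**2. Effect on the treatment estimate.** This was checked by simulation with 100 runs, 78 schools of 166 pupils (SAP Table 4), no true effect and 20 imputations. Assumed: outcome = 0.5 × baseline + 0.4 × auxiliary + school effect (variance 0.015) + residual (SD 0.75), giving a total SD of about 1. Missingness is about 20%, with log-odds rising by 0.6 per SD of the driving variable in the intervention arm only. Bias is relative to the full data; Monte Carlo error is below 0.001.

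| Analysis | Driver: baseline score | Driver: auxiliary |
|---|---|---|
| Complete cases | −0.0008 | −0.0480 |
| Printed rule, primary-model terms kept | −0.0003 | −0.0482 |
| Printed rule, baseline score allowed to drop out | −0.0601 | −0.0477 |
| p < 0.10, primary-model terms kept | −0.0005 | 0.0004 |

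The auxiliary was excluded by the printed rule in every run where it drove missingness. The bias is the auxiliary's coefficient times the between-arm difference in its mean among responders: −0.048 / 0.4 = −0.12 SD. When the dependence is the same in both arms, that difference, and so the bias, is about zero. Imputing only from terms already in the primary model reproduces the complete-case answer; auxiliary variables are what imputation could add.

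**3. Range.** A large-sample version (400,000 pupils, no true effect, 28–31% missing, residual auxiliary–outcome correlation 0.2 to 0.4, all assumed) gave a bias of 0.022–0.047 SD if the link to missingness is halved in one arm and 0.045–0.099 SD if it is absent in one arm. Including the auxiliary left at most 0.004. A repeat at 28–30% missing gave 0.02–0.04 and 0.035–0.08. Against the MDES of 0.094 (SAP Table 4, randomisation column): 0.02 / 0.094 = 0.21 and 0.10 / 0.094 = 1.06, so from about a fifth of the MDES to all of it.

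**4. Loss assumption.** The plan's own figures reproduce with 10% attrition: 1,054 / 0.90 = 1,172 (rounded up per arm), and 1,172 × 5.8 = 6,798. With 20% loss the first would be 1,054 / 0.80 = 1,318. The sample size therefore did not use the 20% stated in 2.3.8. Correcting the inequality changes no stated sample size.

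**The case against.** The strongest reply is that this is a sign slip. The sentence says the variables must be associated, and SAP 2.3.4 uses a 0.1 significance level to decide which factors enter a model. That is probably right and makes the repair easy, but the printed threshold is still the opposite of the stated intent.

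A reader might infer that the planned imputation cannot correct attrition bias at all. The documents do not support that. The primary-model terms enter whatever the screen does, and with them kept the estimate was unbiased when missingness followed the baseline score differently by arm.

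A reader might also take the 24% missing in SAP Table 6 (4,215 of 17,608) as attrition. It is baseline non-response, and Protocol 3.2 places baseline before allocation. No follow-up missingness is reported.

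Nor do the four withdrawals establish outcome loss: SAP 2.2 does not say whether their pupils will be followed up, and Protocol 3.2 plans collection in all schools.

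The remaining statements are real errors of smaller consequence. Every other section gives 15 months. Imputation is triggered by the proportion missing, not by the mechanism regression. Missingness associated with allocation already triggers the pattern-mixture analysis, so the withdrawals may do so, although the SAP does not say this. The 96% relative-efficiency rule gives few imputations (10 at a missing fraction of 0.40). That affects precision, not bias, and asking for more would be a preference.

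**Conclusion.** The threshold is wrong as written, and this does not depend on any assumption. Its consequence is limited: no correction is gained from the screened-out auxiliary variables, while bias explained by arm, baseline score, FSM stratum and school is still handled.

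The 0.02 to 0.10 SD range needs two conditions together: a prognostic variable outside the primary model (assumed residual correlation 0.2 to 0.4) and a link to missingness that differs by arm. The documents establish neither, so the range shows what could be at stake and is not a forecast. The bias could go either way, depending on which arm loses the higher-scoring pupils.

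The inference about mechanism is also wrong. Finding no predictors is compatible with data missing completely at random and cannot exclude missing not at random. The six-month timing and the 20% loss contradict other sections, and the SAP's pattern-mixture trigger is narrower than the protocol's. None of these disables the imputation.

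**What to change.** In SAP 2.3.8:

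1. Change the threshold to p < 0.10. State that the imputation model always includes all primary-model terms, allocation and school, plus already collected baseline and administrative variables (attendance, suspensions, exclusions) associated with missingness or with the outcome.
2. Replace six months with 15 months throughout.
3. Reword the mechanism sentence: finding no predictors is compatible with missing completely at random and does not exclude missing not at random.
4. Align the loss assumption with the 10% attrition and 20% non-consent used in the sample size.
5. Run the pattern-mixture analysis whenever missingness exceeds 5%, as in Protocol 4.1, with a scenario for the four withdrawn intervention schools if their follow-up data are unavailable.

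The cost is SAP wording and some computing time. No new data are needed, because the administrative records are already planned. The changes should be dated before follow-up outcomes are examined.
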